2.3. The Respiratory Syncytial Virus Human Challenge Model

The RSV human challenge model was developed to not only aid understanding of RSV disease, but to also assess the efficacy of RSV antivirals, immunomodulators and vaccines. The RSV-A Memphis 37b challenge strain has been used for over 15 years by both hVIVO and others and has helped assess the efficacy of numerous RSV therapies (as reviewed by [Lambkin-Williams et al, 2018](#); [DeVincenzo et al, 2020a](#); [DeVincenzo et al, 2020b](#); [Stevens et al, 2018](#)) and vaccines ([Sadof et al, 2021](#); [Pfizer 2021](#); [Bavarian Nordic 2021](#)). Specifically, hVIVO have safely and successfully used the RSV challenge strain in over 1400 healthy participants (18 to 60 years of age) including the inoculation of 24 participants between 60 and 75 years of age. Additionally, another clone of the same strain of live RSV (Memphis 37c) has been used as an inoculation agent and was shown to be safe in over 77 healthy young adults across 3 studies. Healthy RSV challenge study participants have approximately 65% to 85% chance of becoming infected with RSV following the administration of the virus ([DeVincenzo et al, 2010](#)). Typical RSV illness is characterised by an abrupt onset of rhinitis, nasal stuffiness, malaise, myalgia (muscle aches), and sore throat. In healthy adults, the illness usually resolves without any treatment, with relief of symptoms occurring naturally within 7 to 10 days. Respiratory syncytial virus, like many viruses, can cause more substantial health issues such as myocarditis (inflammation or damage to the heart muscle). Adults and children present with RSV-related myocarditis rarely, with symptomless occurrences likely going undiagnosed in the community.

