
 To evaluate the effect of RV299 compared to placebo in healthy adult participants inoculated with RSV in terms of antiviral effect assessed by: 
 Viral-load related endpoints. 	
Additional viral load endpoints relating to antiviral effect include, but are not limited to:
 
 Peak viral load of RSV as defined by the maximum viral load determined by qRT-PCR measurements in nasal samples starting from initial administration of IMP up to planned discharge from quarantine (Day 12, am). Time (days) to confirmed negative test by qRT-PCR measurements in nasal samples starting at initial administration of IMP to first confirmed undetectable assessment after peak measure. Time (days) to confirmed negative test by qRT-PCR measurements in nasal samples starting from peak qRT-PCR after initial administration of IMP to first confirmed undetectable assessment after peak measure. Time (days) to peak qRT-PCR in nasal samples, starting from initial administration of IMP. Area under the viral load-time curve (VL-AUC) of RSV challenge virus as determined by viral culture on nasal samples, starting at initial administration

Objectives	Endpoints
	
of IMP up to planned discharge from quarantine (Day 12, am).
 
 Peak viral load of RSV as defined by the maximum viral load determined by viral culture measurements in nasal samples starting from initial administration of IMP up to planned discharge from quarantine (Day 12, am). Time (days) to confirmed negative test by viral culture measurements in nasal samples starting at initial administration of IMP to first confirmed undetectable assessment after peak measure. Time (days) to confirmed negative test by viral culture measurements in nasal samples starting from peak viral culture after initial administration of IMP to first confirmed undetectable assessment after peak measure.

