9.4.2.2. Inferential Statistics and Significance Testing

Between-arm comparisons will be performed using appropriate hypothesis tests at the 5% 2-sided significance level, except if otherwise specified. No adjustment for multiple testing will be performed (see [Section 9.1, Statistical Hypothesis](#)).

For continuous variables (either raw data or log-transformed data) the difference in means, the standard error and the 95% 2-sided CI will be presented. In case of log-transformed variables, in addition to the previous statistics on the log-transformed data, the geometric means and geometric mean ratio and its 95% 2-sided CI for the original variable will be presented. The Wilcoxon rank-sum test, t-test, or analysis of covariance will be used, depending on whether the endpoints are normally distributed. Details on the method used for each endpoint will be provided in the SAP. Methods for checking statistical model assumptions and alternative methods of analysis if the assumptions are not fulfilled will be described in the SAP.

For categorical variables, differences in absolute frequency and/or relative risks will be presented, with their 95% 2-sided CIs. Except otherwise specified in the SAP, the Chi-square test (or Fisher Exact test) will be used to compare frequencies between study intervention arms.

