6. STUDY DESIGN

6.1. Summary of Study Design

This is a single-centre, randomised, double-blind, placebo-controlled, proof-of-concept study in healthy adult male and female participants from 18 to 55 years of age, inclusive. The primary goal of this Phase 1b study is to assess the antiviral activity of RV299 against RSV in the viral challenge model. In addition, the safety, tolerability, and PK of RV299 will be assessed.

A total of 80 participants is planned to be enrolled in this study: 40 participants on RV299 and 40 participants on placebo.

The study is divided into the following study phases:

- Screening phase: from Day -90 to Day-3 pre-human viral challenge (HVC). Historical generic screening data collected through the hVIVO generic screening process may be transferred to this study after the study-specific consent form has been signed by the participant.
- Inpatient phase: Participants will be resident in the quarantine unit for approximately 15 days (from Day -2 to Day 12). Procedures will include:
 - Pre-HVC:
 - Admission to quarantine unit on Day -2/-1.
 - Baseline assessments will be conducted as per Schedule of Events (SoE) up to Day 0, pre-challenge.
 - HVC: RSV-A Memphis 37b virus inoculation on Day 0.
 - Post-HVC:
 - Randomisation to receive RV299 or matched placebo.
 - Administration of IMP (RV299/placebo). Each participant will receive IMP twice daily (~12 hours interval) for 5 consecutive days:
 - IMP dosing to start on confirmation of RSV infection, i.e., after a positive result by qualitative integrative cycler polymerase chain reaction (qicPCR). The qicPCR of nasal wash will be performed twice daily on Days 2-5 (Day 5 morning only), or until a positive result is received, whichever is sooner. The earliest start of IMP dosing will be in the evening of Day 2 post-HVC (IMP will be initiated 12 hours \pm 1-hour post nasal wash confirmation of infection)
 - OR
 - IMP would start in the evening of Day 5, if no positive result obtained by qicPCR
 - Day 1 onwards and each day study assessments will be conducted as per SoE.
 - Participants will be discharged from the quarantine unit on Day 12 (or may remain longer at the discretion of the principal investigator [PI]/investigator).
- Outpatient phase:
 - Final visit: Day 28 (\pm 3 days).

The overall study design is depicted in

Table 1.

Table 1: Study Schematic: On-study Participant Progression

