10.1.4. Statistical Testing and Estimation

Statistical analyses for the primary and secondary endpoints will be performed using appropriate two-sided hypothesis tests at the 5% significance level.

For continuous data, an analysis of covariance (ANCOVA) will be used to compare means between the RV299 and placebo groups. The ANCOVA will have treatment group as a fixed effect and baseline viral load as a covariate, unless stated otherwise in the relevant endpoint section. Should data not satisfy the assumptions, an appropriate alternative test, e.g., Wilcoxon Rank-Sum test will be used.

P-values will be rounded to 4 decimal places. All p-values that round to 0.0000 will be presented as <0.0001 and p-values that round to 1.000 will be presented as >0.9999.

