10.7. Statistical Analysis

All efficacy analyses will be based on the ITT-I population as the primary analysis. Where the populations differ to ITT-I population by 1 participant within a treatment group, the primary and selected secondary analyses will be repeated for the ITT-A, ITT-B, ITT and PP populations. This will be reviewed and documented at the BDRM.

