10.7.2. Secondary Endpoints

10.7.2.3 Viral Load Endpoints

Peak Viral Load of RSV as Defined by the Maximum Viral Load Determined by qRT-PCR Measurements in Nasal Samples Starting from Initial Administration of IMP up to Planned Discharge from Quarantine

Using the scheduled protocol assessments from the last measurement collected prior to the first dose of IMP to morning of Day 12 (Quarantine discharge), the highest qRT-PCR viral load value observed in nasal samples for each participant will be summarised and analysed in a similar fashion to the primary efficacy endpoint described in Section 10.7.1.

Participants who stay undetectable (i.e. a 'Not Detected' value) during quarantine will be replaced with the 'Not Detected' value shown in the table in Appendix 15.1.

Time to Confirmed Negative Test by qRT-PCR Measurements in Nasal Samples Starting from Initial Administration of IMP to First Confirmed Undetectable Assessment after Peak Measure

The time from the first administration of IMP to the first confirmed negative qRT-PCR test after the peak qRT-PCR measurement will be calculated in days as:

Date and time of first confirmed negative test after peak qRT-PCR measurement – Date of and time of first IMP administration.

A negative test is defined as two consecutive 'Not Detected' results in the qRT-PCR test, with the date and time of the first negative test being utilised in the calculations. The peak qRT-PCR is defined as the highest viral load value obtained by a participant after their first administration of IMP.

Participants who did not have a confirmed undetectable assessment after first administration of IMP are censored at their last detectable assessment after their peak qRT-PCR measurement. Participants who stay undetectable during quarantine will be excluded from this analysis. Participants who return a positive result after two consecutive 'not detected' results will remain within the analysis.

The time to confirmed negative test will be summarised descriptively by treatment group. Kaplan Meier [2] curves will be produced for each treatment group, overlayed on one plot. A supporting table will include the median, 25th and 75th percentiles for each group and will be accompanied by a log rank test to compare between RV299 and placebo with the corresponding p-value presented.

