Table 14.2.2.5.4	AUC of RSV Challenge Virus Viral Load by Viral Culture from Initial Administration of IMP to Quarantine Discharge (Untransformed Data) - ITT-I Population
Table 14.2.2.6	Peak Viral Load of RSV Challenge Virus by Viral Culture from Initial Administration of IMP to Quarantine Discharge - ITT-I Population

Where appropriate, these tables may be repeated on the ITT-A, ITT-B, ITT and PP Populations as .2, .3, .4 and .5 respectively.

Programming Note: It is possible that the parametric methods will fail to meet the required assumptions for the main or repeated tables. Therefore, we will provide a Wilcoxon test (see Section 10.1.4). The alternative presentation for this is shown below and will require the following footnote to be updated: [1] Comparison of RV299 and placebo using a Wilcoxon rank sum test.

Median difference in LS means [1] XX.XX
P-value [1] X.XXX

Table 14.2.2.2.1
Time to First Confirmed Undetectable Assessment of RSV Challenge Virus by qRT-PCR from Initial Administration of IMP
ITT-I Population

Time (days)	Treatment Group					
	RV299 (N=xx)			Placebo (N=xxx)		
	n	N#	Kaplan-Meier Estimate	n	N#	Kaplan-Meier Estimate
X	xx	xx	0.xxxx	xx	xx	0.xxxx
X	xx	xx	0.xxxx	xx	xx	0.xxxx
X	xx	xx	0.xxxx	xx	xx	0.xxxx
X	xx	xx	0.xxxx	xx	xx	0.xxxx
X	xx	xx	0.xxxx	xx	xx	0.xxxx
X	xx	xx	0.xxxx	xx	xx	0.xxxx
X	xx	xx	0.xxxx	xx	xx	0.xxxx
X	xx	xx	0.xxxx	xx	xx	0.xxxx
X	xx	xx	0.xxxx	xx	xx	0.xxxx
X	xx	xx	0.xxxx	xx	xx	0.xxxx
X	xx	xx	0.xxxx	xx	xx	0.xxxx
X	xx	xx	0.xxxx	xx	xx	0.xxxx
X	xx	xx	0.xxxx	xx	xx	0.xxxx
25 th percentile [1]		xx.x			xx.x	
50 th percentile [1]		xx.x			xx.x	
75 th percentile [1]		xx.x			xx.x	
p-value [2]		xxxxx				

n = number of participants with a confirmed undetectable assessment by the end of the period. N# = number of participants at risk.

[1] Percentiles are obtained from the Kaplan-Meier estimates.

[2] P-value obtained from a log-rank test compared RV299 and placebo.

Note: Time to First Confirmed Undetectable Assessment from Initial Administration of IMP = (Date of first confirmed negative test after peak qRT-PCR measurement - Date of first administration of IMP) + 1.

This table may be repeated on the ITT-A, ITT-B, ITT and PP Populations as .2, .3, .4 and .5 respectively.

This layout will be utilised for the following tables:

Table 14.2.2.3.1 Time to First Confirmed Undetectable Assessment of RSV Challenge Virus after Peak Measure by qRT-PCR from qRT-PCR following Initial Administration of IMP - ITT-I Population

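### The four time-to-negative endpoints get an unadjusted log-rank p-value but no between-arm estimate or confidence interval, so a non-significant result would be hard to interpret.

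*Protocol*

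**What the plan says.** Protocol Section 3 sets the objective of evaluating the effect of RV299 against placebo on viral-load endpoints, among them "Time (days) to confirmed negative test by qRT-PCR measurements in nasal samples starting at initial administration of IMP to first confirmed undetectable assessment" after the peak. The other three are the from-peak version and the same pair by viral culture. Protocol Table 9-2 planned no inferential analysis for the time-to-negative endpoints it lists (it shows no row for the qRT-PCR from-peak version). SAP Section 11 declares a change and adds log-rank tests.

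In SAP 10.7.2.3 each of the four has a descriptive summary, overlaid Kaplan-Meier curves and a supporting table of per-arm median and quartiles, "accompanied by a log rank test to compare between RV299 and placebo with the corresponding p-value presented". The Table 14.2.2.2.1 shell, whose layout serves all four, has Kaplan-Meier estimates, three percentiles per arm and one p-value, footnoted "P-value obtained from a log-rank test compared RV299 and placebo". It has no row for a hazard ratio, a difference or an interval. The test has no strata and no covariate.

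The continuous endpoints are treated differently. SAP 10.1.4 states: "The ANCOVA will have treatment group as a fixed effect and baseline viral load as a covariate". SAP 10.7.1.1 then reports an LS mean difference with a two-sided 95% interval and defines baseline as the last qRT-PCR value before first IMP.

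**The concern.** A p-value does not measure an effect. Protocol 9.4.2.2 attaches 95% intervals to between-arm results for continuous and categorical variables. When the SAP added a test for the time-to-negative endpoints, it did not add an estimate and interval to go with it. In a trial this small, a real effect on clearance could easily miss significance. The report would then show a p-value and two sets of quartiles, with nothing to say which effect sizes the data exclude.

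The secondary question is adjustment. The baseline covariate is already collected, defined and used for the primary endpoint, but is left out here. If it predicts clearance, using it would also recover some power.

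**Working it through.** **Nothing to reproduce.** The visible text gives no power, event count or effect size for these endpoints. The part of the protocol between 9.1 and 9.3 is redacted, so its absence is not a criticism. The figures below are illustrative.

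**Inputs from the documents**
- Sample size: "A total of 80 participants is planned to be enrolled in this study: 40 participants on RV299 and 40 participants on placebo" (SAP 6.1).
- Analysis set: "All efficacy analyses will be based on the ITT-I population as the primary analysis" (SAP 10.7).
- Infection rate: "Healthy RSV challenge study participants have approximately 65% to 85% chance of becoming infected with RSV following the administration of the virus" (Protocol 2.3).
- Two-sided 5% level (Protocol 9.4.2.2; SAP 10.1.4).

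**Assumed.** The cited infection rate gives the ITT-I size; 50%, 70% or 90% of ITT-I reach negative by the morning of Day 12; hazard ratio 1.5 or 2.0.

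**Step 1, analysis set.** 0.65 × 80 = 52 and 0.85 × 80 = 68.

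**Step 2, log-rank power and precision for d events, 1:1.**
- Power = Φ(½√d × ln HR − 1.96).
- Smallest HR with 80% power = exp(2 × (1.96 + 0.84)/√d).
- 95% interval for the HR ≈ estimate divided and multiplied by exp(1.96 × 2/√d).

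Worked case: 52 × 0.5 = 26 events. ½ × 5.099 × 0.693 − 1.96 = −0.19, so power is 42% at HR 2.0.

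| ITT-I | Reaching negative | Events | Power, HR 1.5 | Power, HR 2.0 | HR for 80% power | Interval factor |
|---|---|---|---|---|---|---|
| 52 | 50% | 26.0 | 18% | 42% | 3.00 | 2.16 |
| 52 | 90% | 46.8 | 28% | 66% | 2.27 | 1.77 |
| 60 | 70% | 42.0 | 26% | 61% | 2.37 | 1.83 |
| 68 | 50% | 34.0 | 22% | 52% | 2.61 | 1.96 |
| 68 | 90% | 61.2 | 35% | 77% | 2.05 | 1.65 |

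By the same formula, 80% power needs 66 events at HR 2.0 and 191 at HR 1.5. As an illustration, an observed HR of 1.6 on 42 events would have an interval of 1.6/1.83 = 0.87 to 1.6 × 1.83 = 2.93. That is non-significant, yet compatible with nearly a threefold rate of clearance. The planned table would not show this.

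**Step 3, effect of adjusting for baseline.** Simulation assumptions: 60 infected, 12-hourly sampling with ties, log HR 0.8 conditional on baseline. Power is log-rank / Cox with Efron ties.

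| Baseline log HR per SD | 500 trials per setting | 1,500 trials per setting |
|---|---|---|
| 0 | 78% / 78% | 83% / 81% |
| 0.2 | 81% / 80% | 79% / 81% |
| 0.4 | 75% / 79% | 76% / 81% |
| 0.6 | 65% / 80% | 66% / 81% |

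Simulation error at 80% power is √(0.8 × 0.2/500) ≈ 2 points and √(0.8 × 0.2/1,500) ≈ 1 point. The gain is therefore nil at 0 to 0.2, about 4 to 5 points at 0.4 and about 15 points at 0.6. Type I error in the 1,500-trial runs was 4% to 6% for both methods.

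Tie handling matters. With Breslow ties, adjustment lost about 3 to 6 points at 0 to 0.2 and was level at 0.4.

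**Step 4, from-peak formulas.** In SAP 10.7.2.3 both from-peak endpoints (qRT-PCR and culture) are described as time from the peak, but their formulas subtract the date and time of first IMP administration. An effect estimate from those formulas would not describe the endpoint named.

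**The case against.** Several stronger readings are tempting, and the documents do not support them.

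- A reader might infer that the size of any speed-up is never reported. Per-arm medians, quartiles and overlaid curves are planned, so a crude difference can be read where both medians are reached. SAP 10.1.2 also allows intervals for a mean or median where appropriate, although the shell for these endpoints does not apply it. What is missing is a formal contrast and its precision.
- A reader might infer that omitting baseline loses power. The documents give no association between baseline viral load and clearance, and Step 3 shows no gain when it is weak.
- A reader might assume that a higher baseline means further to fall. Dosing is triggered by the first positive qicPCR, often before the peak, and only a negative test after the peak counts. In a toy rise-and-fall model with assumed kinetics, higher baseline went with the same or a shorter time (correlations −0.42 to −0.01). The direction is uncertain. Adjustment can use an association in either direction, but a single linear term may fit imperfectly.
- The log-rank test is valid, and adding it is a declared change. The adjusted hazard ratio is conditional on baseline. It differs from the marginal contrast and should be labelled as such.

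It is also fair to say that these are secondary endpoints in an early-phase study without multiplicity control, and that the primary AUC already has an adjusted difference with an interval. That limits the consequence. It does not remove the gap, because the case for an interval in Step 2 does not depend on how prognostic baseline is.

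**Conclusion.** The point holds as a gap in estimation. For all four time-to-negative endpoints, the SAP offers an unadjusted log-rank p-value as the sole between-arm result, without an estimate or interval. At 52 to 68 infected and an assumed 50% to 90% reaching negative, power is about 42% to 77% at HR 2.0 and 18% to 35% at HR 1.5. Non-significant results are therefore likely even if a useful effect exists. An interval would run from the estimate divided by about 1.65 to 2.16 to the estimate multiplied by the same factor.

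The benefit of adjusting for baseline is conditional on a prognostic strength that the documents do not give, so it is a reasonable addition and not a demonstrated power loss. The effect is on the interpretation of secondary endpoints only.

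**What to change.** In SAP 10.7.2.3, keep the Kaplan-Meier curves and the log-rank test for each time-to-negative endpoint. Add a Cox model with treatment and the last pre-dose qRT-PCR viral load, and report the hazard ratio with its 95% interval. Specify Efron or exact ties, because sampling is about 12-hourly. Add the hazard ratio and interval rows to the Table 14.2.2.2.1 shell. Time to peak by qRT-PCR shares that layout, so state whether the new rows apply to it.

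Before that, correct the two from-peak formulas so that they subtract the time of the peak.

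The cost is one extra model and two table rows per endpoint, with no new data. The model relies on roughly proportional hazards and uses one degree of freedom. The log-rank result remains available if that assumption looks doubtful.

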
 To evaluate the safety of multiple orally administered doses of RV299 when compared to placebo. 	
 Safety data including, but not limited to, occurrence of AEs from initial administration of IMP up to the Day 28 follow-up. Occurrence of SAEs from initial administration of IMP up to the Day 28 follow-up.

 To monitor the safety of the challenge virus. 	
 Occurrence of AEs related to the viral challenge from viral challenge (Day 0) up to the Day 28 follow-up. Occurrence of SAEs related to the viral challenge from viral challenge (Day 0) up to the Day 28 follow-up. Use of concomitant medications from viral challenge (Day 0) up to the Day 28 follow-up.

Objectives	Endpoints

Pharmacokinetics
	

 • To characterise the PK profile of RV299 after a single oral dose and after multiple oral doses in plasma from healthy participants inoculated with RSV. 	
Secondary endpoints related to PK include, but are not limited to:
 
 • Time to maximum plasma concentration (t_{max}), terminal half-life ($t_{1/2}$), C_{max}, area under the plasma concentration-time curve from time zero to the end of the dosing interval (AUC_{τ}), AUC_{0-24h}, and area under the plasma concentration-time curve from time zero to infinity ($AUC_{0-\infty}$).

CCI
 	
	
	
	
	
	
	
	
	
	
	
	
	
	
	
	
	
	
	
	
	
	
	
	
	
	
	
	
	
	
	
	
	
	
	
	
	
	
	
	
	
	
	
	
	
	
	
	
	
	
	
	
	
	
	
	
	
	
	
	
	
	
	
	
	
	
	
	
	
[figure not shown] Females of childbearing potential must have a negative pregnancy test prior to enrolment. Females of non-childbearing potential: 
 Post-menopausal females defined as amenorrhea for ≥ 12 months with no alternative medical cause. A high follicle-stimulating hormone (FSH) level, within appropriate post-menopausal range, may be used to confirm post-menopausal state in the absence of combined hormonal contraception or hormone replacement therapy. If there is < 12 months of amenorrhea 2 FSH samples are required at least 4 to 6 weeks apart. Documented status as being surgically sterile (e.g., tubal ligation, hysterectomy, bilateral salpingectomy, and bilateral oophorectomy).

No.	hVIVO APPROVED STANDARD INCLUSION CRITERIA (Viral Challenge Volunteer Studies) Final v11.0, 08FEB2022

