10.9.1. Adverse Events

All adverse events (AE) will be coded using MedDRA, Version 25.0.

An adverse event is defined as treatment emergent if the onset date is on or after the date of first dosing with IMP. Should any onset date for an adverse event be missing or only a partial date recorded (such that it cannot be determined if the event onset was prior to start of IMP or not) then it will be assumed that the event is treatment emergent, unless the adverse event stop date indicates otherwise.

Similarly, an AE is defined as challenge emergent if the onset date is on or after the date of inoculation. Should any onset date for an adverse event be missing or only a partial date recorded (such that it cannot be determined if the event onset was prior to inoculation or not) then it will be assumed that the event is challenge emergent, unless the adverse event stop date indicates otherwise.

An AE can be both challenge emergent and treatment emergent. Any AE with an onset date earlier than the inoculation date will be classified as a pre-treatment AE.

If a participant experiences more than one adverse event with the same preferred term, that preferred term will be counted only once. It will be assigned the greatest observed severity and the strongest relationship to IMP among those events for the tables in which those characteristics are summarised.

Pre-treatment AEs will be identified in a patient listing.

A summary of treatment-emergent AEs will be presented by treatment group showing the number of events, number of participants with events (also split by severity; mild, moderate, severe), number of participants with SAEs, number of participants with related events, number of participants with events

leading to early withdrawal from the study and the number of participants with events leading to early discontinuation of IMP.

Further summaries will present the treatment-emergent AEs by:

- Treatment group, SOC and PT.
- Treatment group, SOC, PT and severity.
- Treatment group, SOC, PT and relationship to IMP.

Further summaries will present the challenge-emergent AEs by:

- Treatment group, SOC, PT and relationship to challenge agent.

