Min, Max	XX, XX	XX, XX		XX, XX	XX, XX
[Repeat for all days during Quarantine Period]					

Note: Days are relative to first administration of IMP.

Note: Total symptom scores on the day of the first administration of IMP can be prior to or after dosing, depending on whether dosed in the morning or evening.

Table 14.2.3.7.1
 Time to Symptom Resolution by 10-Item Diary Card from Initial Administration of IMP to 24-Hours Symptom Free
 ITT-I Population

Time (days)	Treatment Group	
	RV299 (N=xx)	Placebo (N=xx)
n	XX	XX
Mean (SD)	XX.X (XX.XX)	XX.X (XX.XX)
GM (GSD)	XX.X (XX.XX)	XX.X (XX.XX)
%CV	XX.XX	XX.XX
Median	XX.X	XX.X
Q1, Q3	XX.X, X.XX	XX.X, X.XX
Min, Max	XX, XX	XX, XX

Note: Time to Symptom Resolution from Initial Administration of IMP = (Date and time of symptom resolution - Date of and time of assessment at time of IMP administration) + 1.

This layout will be utilised for the following tables:

Table 14.2.3.8.1 Time to Symptom Resolution by 10-Item Diary Card from Peak Total Symptom Score to 24-Hours Symptom Free - ITT-I Population
 Table 14.2.3.9.1 Time to Peak Symptom Score by 10-Item Diary Card from Initial Administration of IMP - ITT-I Population

The layout will be repeated for the following tables, without the GM (GSD) row:

Table 14.2.4.1.1 Total Weight of Mucus Produced from Initial Administration of IMP to Quarantine Discharge - ITT-I Population
 Table 14.2.4.2.1 Total Number of Tissues Used from Initial Administration of IMP to Quarantine Discharge by Assessment - ITT-I Population

CCI

Table 14.3.1.67
 Overall Summary of Treatment Emergent Adverse Events
 Safety Population

	Treatment Group					
	RV299 (N=xx)		Placebo (N=xxx)		Overall (N=xx) (%)	
	n	(%)	n	(%)	n	(%)
Number of Events	XX		XX		XX	
Number of Participants with any Adverse Event	XX	(XX.X)	XX	(XX.X)	XX	(XX.X)
Mild	XX	(XX.X)	XX	(XX.X)	XX	(XX.X)
Moderate	XX	(XX.X)	XX	(XX.X)	XX	(XX.X)
Severe	XX	(XX.X)	XX	(XX.X)	XX	(XX.X)
Number of Participants with any Serious Adverse Event	XX	(XX.X)	XX	(XX.X)	XX	(XX.X)
Number of Participants with any Related Adverse Event	XX	(XX.X)	XX	(XX.X)	XX	(XX.X)
Number of Participants with any Adverse Event Leading to Withdrawal from the Study	XX	(XX.X)	XX	(XX.X)	XX	(XX.X)
Number of Participants with any Adverse Event Leading to Discontinuation of IMP	XX	(XX.X)	XX	(XX.X)	XX	(XX.X)

Note: Treatment emergent events are those events with an onset on or after the start of IMP dosing.

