Note: Percentages are based on the safety population.

Table 14.3.1.4
Treatment Emergent Adverse Events Related to RV299 by System Organ Class and Preferred Term
Safety Population

System Organ Class/ Preferred Term [1]/ Relationship	Treatment Group			
	RV299 (N=xx)	n (%)	Placebo (N=xxx)	n (%)
System Organ Class 1	XX	(XX.X)	XX	(XX.X)
Not Assessed	XX	(XX.X)	XX	(XX.X)
Unlikely Related	XX	(XX.X)	XX	(XX.X)
Possibly Related	XX	(XX.X)	XX	(XX.X)
Probably Related	XX	(XX.X)	XX	(XX.X)
Definitely Related	XX	(XX.X)	XX	(XX.X)
Preferred Term 1	XX	(XX.X)	XX	(XX.X)
Not Assessed	XX	(XX.X)	XX	(XX.X)
Unlikely Related	XX	(XX.X)	XX	(XX.X)
Possibly Related	XX	(XX.X)	XX	(XX.X)
Probably Related	XX	(XX.X)	XX	(XX.X)
Definitely Related	XX	(XX.X)	XX	(XX.X)
Preferred Term 2	XX	(XX.X)	XX	(XX.X)
Not Assessed	XX	(XX.X)	XX	(XX.X)
Unlikely Related	XX	(XX.X)	XX	(XX.X)
Possibly Related	XX	(XX.X)	XX	(XX.X)
Probably Related	XX	(XX.X)	XX	(XX.X)
Definitely Related	XX	(XX.X)	XX	(XX.X)
System Organ Class 2	XX	(XX.X)	XX	(XX.X)
Not Assessed	XX	(XX.X)	XX	(XX.X)
Unlikely Related	XX	(XX.X)	XX	(XX.X)
Possibly Related	XX	(XX.X)	XX	(XX.X)
Probably Related	XX	(XX.X)	XX	(XX.X)
Definitely Related	XX	(XX.X)	XX	(XX.X)
Preferred Term 1	XX	(XX.X)	XX	(XX.X)
Not Assessed	XX	(XX.X)	XX	(XX.X)
Unlikely Related	XX	(XX.X)	XX	(XX.X)
Possibly Related	XX	(XX.X)	XX	(XX.X)
Probably Related	XX	(XX.X)	XX	(XX.X)
Definitely Related	XX	(XX.X)	XX	(XX.X)

[1] MedDRA Version 25.0.

Note: Treatment emergent events are those events with an onset on or after the first administration of IMP.

Note: This table shows distinct number of participants with events for each system organ class/preferred term/relationship. If a participant experiences a specific event more than once then the event with the greatest relationship is summarised.

Note: Only the subset of AEs that are judged to be related to IMP have been considered (i.e. relationship = Possibly Related/Probably Related/Definitely Related/Not Assessed) in the table.

Note: Percentages are based on the safety population.

This layout will be utilised for the following table:

Table 14.3.1.5 Adverse Events Related to Challenge Agent by System Organ Class and Preferred Term - Safety Population

With the following footnote:

Note: Only the subset of AEs that are judged to be related to challenge agent have been considered (i.e. relationship = Possibly Related/Probably Related/Definitely Related/Not Assessed) in the table.

Table 14.3.2
Haematology Parameters: Summary
Safety Population

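### Challenge-related SAEs from Day 0 to Day 28 are a named secondary endpoint, but no planned SAP table counts them

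*Protocol*

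**What the plan says.** Protocol Section 3 sets an objective of monitoring the safety of the challenge virus. Two of its endpoints are event occurrences: challenge-related AEs, and "Occurrence of SAEs related to the viral challenge from viral challenge (Day 0) up to the Day 28 follow-up". SAP Section 7.2 carries both forward. SAP Section 11, which lists six changes from the protocol analysis, does not drop or redefine either.

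SAP Section 10.9.1 plans the AE outputs:

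- **Overall summary (Table 14.3.1.1).** "A summary of treatment-emergent AEs will be presented by treatment group showing the number of events, number of participants with events"; it also gives participants with SAEs. The shell row is "Number of Participants with any Serious Adverse Event", and its note reads "Treatment emergent events are those events with an onset on or after the start of IMP dosing".
- **Treatment-emergent rule.** "An adverse event is defined as treatment emergent if the onset date is on or after the date of first dosing with IMP".
- **Challenge-emergent events.** These are defined by onset from the inoculation date. They have a single summary, by "Treatment group, SOC, PT and relationship to challenge agent". It becomes Table 14.3.1.5, "Adverse Events Related to Challenge Agent by System Organ Class and Preferred Term - Safety Population", which reuses the shell of Table 14.3.1.4.

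All safety presentations use the Safety Population (SAP Section 10.9). SAP Section 9.6 limits that to randomised, inoculated participants who received IMP at least once.

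**The concern.** In a challenge trial, healthy volunteers are deliberately infected. How many had a serious event attributed to the virus is a result in its own right, and the trial has declared it as an endpoint. A reader of the study report would look for one line with that number, by arm and overall. Followed as written, the SAP does not produce it. The line that looks closest, the SAE row in Table 14.3.1.1, has a different start date and a different attribution. It could show zero when a challenge-related SAE had occurred before dosing began.

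**Working it through.** The plan states no figure for this point, so the check is to trace the endpoint through the planned outputs.

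**What the endpoint needs:** seriousness, relationship to the challenge agent, onset from Day 0 to Day 28, and a count of participants.

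| Output | Onset from | Serious? | Challenge relationship? | Any-event row? |
|---|---|---|---|---|
| Table 14.3.1.1 | first IMP | yes, any cause | no | yes |
| Table 14.3.1.2 | first IMP | no | no | yes |
| Table 14.3.1.3 | first IMP | no | no | no |
| Table 14.3.1.4 | first IMP | no | no (relationship to IMP) | no |
| Table 14.3.1.5 | inoculation | no | yes | no |
| Listing 16.2.7 | all AEs, with both emergence flags | yes | yes | not a summary |

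No table combines seriousness with challenge relationship. Only the listing does.

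**Dates left out of the SAE row.** Under the date rule in SAP Section 10.9.1, a first dose on Day d excludes onset dates Day 0 to Day d − 1, which is d dates. SAP Section 6.1 puts the first dose between the evening of Day 2 and the evening of Day 5.

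- d = 2: Days 0-1, at most 2 dates.
- d = 5: Days 0-4, at most 5 dates.

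These are maxima, because part of Day 0 precedes inoculation. The shell note speaks of the start of dosing. Read by clock time, it would also exclude the hours before an evening first dose.

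**Following three hypothetical challenge-related SAEs:**

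1. *Onset Day 1, first dose Day 2.* Not in Table 14.3.1.1. In Table 14.3.1.5 as a preferred term, with nothing to mark it serious.
2. *Onset Day 7, after dosing began.* In Table 14.3.1.1 among SAEs of any cause. In Table 14.3.1.5, again not marked serious.
3. *Onset Day 1, never dosed.* Outside the Safety Population, so in no safety table. SAP Section 10.1.2 puts all collected data in listings, so it should appear in Listing 16.2.7.

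**Why Table 14.3.1.5 cannot be summed to a participant total.** Its layout starts at the first system organ class. A participant with events in two classes adds 1 to each, so the rows sum to 2 for 1 participant. The any-event row that would settle this is in the Table 14.3.1.2 shell but not in this one.

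**'Related' has two meanings.** SAP Section 10.9.1 and the Table 14.3.1.1 note include 'Unlikely'. The footnotes to Tables 14.3.1.4 and 14.3.1.5 omit it, although the layout has an 'Unlikely Related' row. A new challenge-related count could therefore come out as two different numbers.

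**The case against.** The best defence is that nothing is lost. Listing 16.2.7 shows, event by event, the SAE flag, the serious criteria, the challenge-emergent flag, the onset and the relationship to the challenge agent. Safety analysis is descriptive only, and with few SAEs expected a hand tally is easy. Participant protection does not depend on these tables: unexpected virus-related SAEs fall under the third stopping-rule status in Protocol Section 7.5, and SAE reporting runs separately. A zero in Table 14.3.1.1 would also not be false, because the title and note state its window. All of this stands. It limits the point to a missing summary, but it does not supply the count that the endpoint calls for.

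Two stronger readings are tempting. A reader might infer that neither challenge-safety occurrence endpoint receives any figure. That is not so: Table 14.3.1.5 gives participant counts and percentages for challenge-related AEs by class and term, and the protocol promises no overall proportion. The any-event row would be an improvement to that table; its absence does not leave the AE endpoint unreported. A reader might also take the defect to be only the few days before dosing, and size it as a share of follow-up or as a shift in an upper confidence bound. The documents do not support that. SAEs after dosing are not split by challenge relationship either, and neither document plans a confidence bound for SAEs.

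**Conclusion.** The point holds for one secondary safety endpoint. Challenge-related SAEs get no summary count in any part of the Day 0 to Day 28 window. Before the first-dose date (at most 2 to 5 dates per participant) they are outside the SAE row altogether; after it they are inside but not attributed to the virus. Inoculated participants who are never dosed are outside every safety table. No efficacy result, test or data collection is affected, and the individual events remain visible in the listing.

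This assumes that no redacted table supplies the count. That is likely: the AE tables in SAP Section 13.2 run unbroken from 14.3.1.1 to 14.3.1.5, and the redacted rows come before them. It also assumes that the date rule in Section 10.9.1 governs over the looser shell note.

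**What to change.** In SAP Sections 10.9.1 and 13.2 and in the shells:

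1. Add one overall summary of challenge-emergent AEs, with onset from inoculation to Day 28. Rows: participants with any challenge-related AE, the same by worst severity, participants with any SAE, and participants with any challenge-related SAE.
2. Add an any-event row at the top of Table 14.3.1.5.
3. Base both tables on all inoculated participants: by arm where randomised, with undosed or unrandomised participants in the total column. Section 10.9.1 already promises a total column in every AE table, and the disposition shell already counts those who received the challenge agent.
4. Choose one definition of 'related', and make the Section 10.9.1 text, the Table 14.3.1.1 note and the footnotes to Tables 14.3.1.4 and 14.3.1.5 agree on whether 'Unlikely' is included.

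The cost is one extra table, one extra row and some wording, best settled before unblinding. The fields needed are already in Listing 16.2.7, so no new data are required.
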